| CT imaging (neck, chest, abdomen, and pelvis) with oral and IV contrast | CT scan with IV contrast (oral if IV is contraindicated) of the neck, chest, abdomen, and pelvis and any other disease sites present at Screening. MRI only for disease sites that cannot be adequately imaged using CT. Brain MRI required only if clinically indicated. | X (imaging part of standard assessments; within 6 weeks prior to dosing is acceptable) | | Q5cycles (starting cycle 5) for first 15 months, thereafter Q12 cycles until PD. After clinical cutoff, disease assessments to be performed Q12 cycles or per local standards (but at a minimum of Q26 weeks). To be performed at the time of atypical responses 'tumor flare'. The same imaging technique used at Screening should be used throughout the study. Results are preferably available before start of treatment in the following cycle. During Follow-up, to be performed at PD and at least Q6 months up to PD or start of subsequent therapy | |
| Whole body FDG-PET scan | For NHL assessments, PET scan at baseline is recommended but not mandatory. Maximal tumor reduction: eg CR or 2 consecutive CT scans showing no further tumor reduction. | X | | at the time of maximal tumor reduction, relapse from CR | |
| Evaluation of other sites of disease | May be performed by radiological imaging, physical examination, or other procedures as necessary | as clinically indicated | | as clinically indicated, using the same method of assessment as used at Screening | |

| | Notes | Screening Period | Treatment Period (14 day cycles) | | | Follow-up Period ^a |
|---|---|---|---|--------------------------|-----|-------------------------------|
| | | up to 28 days before start of any study treatment | BASELINE ASSESSMENT CID1 (without run-in phase) CID-7 (with run-in phase) | Day 1, subsequent cycles | EOT | Q3m |

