Preliminary activity and clinical response will be evaluated every 5 cycles for the first 15 months, thereafter every 12 cycles until progression, at the end of treatment, and every 6 months in follow-up, in the event the subject has not progressed while on therapy and did not start subsequent therapy. Lymphoma including Richter syndrome will be evaluated for response according to the Lugano Classification (Cheson 2014);¹² CLL will be evaluated according to International Workshop on Chronic Lymphocytic Leukemia (IWCLL) (Hallek 2008), see Section 10.1.²³ Identical methodology should be used for disease assessment at baseline and throughout the course of the study.

Subjects will be assigned to receive oral daily doses of ibrutinib (self-administered) in combination with intravenous nivolumab on Day 1 of each cycle starting from Dose Level 1 ([Table 4](#)). In Cohort B1 and B2, to assess pharmacokinetic and pharmacodynamic characteristics of ibrutinib monotherapy, ibrutinib will be given at the recommended Phase 2 dose over an initial period of seven days prior to the first dose of nivolumab (Day -7 to -1). Refer to the Dosage and Administration schedule (Section 6) for further detail. Protocol specified treatment modifications for ibrutinib and nivolumab will be implemented as necessary (Section 6.4). Additional dosing or schedule changes for ibrutinib or nivolumab can be requested by the Study Evaluation Team (SET) based on preliminary clinical data during dose optimization. Doses may be held or reduced based on the severity of and the recovery from previous toxicity. Dose re-escalation may be allowed after

recovery from toxicity following consultation with the Sponsor. In Part A intra-patient dose escalation may be requested by the investigator and discussed with the medical monitor once a subsequent higher combination dose has been declared acceptable by the SET for subjects who (1) have received at least 4 cycles of combination treatment at the assigned dose level, and (2) have not experienced a DLT or therapy-related SAE. Subjects whose dose has been escalated will not be considered for the safety evaluation in the subsequent dose level and the determination of the RP2D.

The study treatment will be continued until:

- documented confirmed disease progression (except in cases of clinical improvement/stability; see Section 11.2)
- unacceptable toxicity
- intercurrent illness that prevents further administration of treatment

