10. STUDY EVALUATIONS

10.1. Efficacy (Assessment of Disease Response and Progressive Disease)

Efficacy assessments will be performed as outlined in Time and Events Schedule ([Table 1](#)). These assessments are to be conducted until disease progression (even if subsequent therapy is started prior to objective disease progression), withdrawal of consent from study participation, or the end of study. For subjects who discontinue study drug before disease progression is documented, disease assessments will continue in the Follow-up Period at least every 6 months until disease progression is documented or the start of subsequent therapy. The determination of disease status for continuation of treatment will be assessed by the investigator at the site based on the results of the efficacy assessments; the results will be recorded in the eCRF. Radiological and PET scans performed prior to the database lock for the final analysis may be transferred to the independent imaging laboratory for storage; the scans may be reviewed, if deemed necessary.

For all subjects, as soon as disease progression is confirmed the sponsor's study lead should be informed immediately. A tumor biopsy should be collected for biomarker evaluations at progression, depending on the indication and if clinically feasible.

The detailed description of efficacy measurements that will be obtained during the study are provided in [Attachment 5](#). At all times, identical methodology should be used for disease assessment at baseline and throughout the course of the study.

The investigator will perform tests that will allow evaluation of response to therapy according to corresponding disease criteria in [Table 21](#).

Table 21: Response Criteria

| Criteria | PART A | PART B | Attachment |
|--|---|----------------------------------|------------|
| IWCLL ¹ | Subjects with CLL | Cohort B1 (CLL) | 6.1 |
| Response Assessment of Non-Hodgkin Lymphoma² | Subjects with B-cell NHL, including SLL | Cohorts B1 (SLL), B2, B3, and B4 | 6.2 |

¹ International Workshop on Chronic Lymphocytic Leukemia (Hallek 2008)²³

² Recommendations for Initial Evaluation, staging and Response Assessment of Hodgkin and Non-Hodgkin Lymphoma: The Lugano Classification (Cheson 2014)¹²

The efficacy endpoints are defined as follows, based on the IWCLL or the Lugano Classification by Cheson (2014),¹² as appropriate for the disease:

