Subjects who discontinue treatment prior to disease progression (for other reasons such as an adverse event) must continue to have regularly scheduled CT scans/efficacy assessments every 10 weeks up to 15 months after the start of study drug. Thereafter, scan will be performed every 24 weeks until disease progression, or death, or the end of the study, whichever occurs first. It is important that instances of progressive disease be reported to the sponsor's medical monitor within 24 hours by means of a form provided by the sponsor (see Contact Information pages provided separately).

Definition of Measurable and Assessable Disease

Eligible subjects must have at least 1 measurable site of disease. Measurable sites of disease are defined as lymph nodes, lymph node masses, or extranodal sites of lymphoma. Each measurable site of disease must be greater than 1.5 cm in the long axis regardless of short axis measurement or greater than 1.0 cm in the short axis regardless of long axis measurement, and clearly measurable in 2 perpendicular dimensions. Measurement must be determined by imaging evaluation. All other sites of disease are considered assessable, but not measurable.

Up to 6 measurable sites of disease, clearly measurable in 2 perpendicular dimensions, will be followed for each subject. Measurable sites of disease should be chosen such that they are representative of the subject's disease (this includes splenic and extranodal disease). If there are lymph nodes or lymph node masses in the mediastinum or retroperitoneum larger than 1.5 cm in 2 perpendicular dimensions, at least 1 lymph node mass from each region should always be included. In addition, selection of measurable lesions should be from as disparate regions of the body as possible.

All other sites of disease will be considered assessable. Assessable disease includes objective evidence of disease that is identified by radiological imaging, physical examination, or other procedures as necessary, but is not measurable as defined above. Examples of assessable disease include bone lesions; mucosal lesions in the GI tract; effusions; pleural, peritoneal, or bowel wall thickening; disease limited to bone marrow; and groups of lymph nodes that are not measurable but are thought to represent lymphoma. In addition, if more than 6 sites of disease are measurable, these other sites of measurable disease may be included as assessable disease.

Positron Emission Tomography (PET Scan)

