1.2. Trial Design

This is an open-label Phase 1/2a study, which consists of Part A (Dose Optimization Cohorts A1 and A2) and Part B (Expansion Cohorts B1, B2, B3 and B4). In the context of this study, a treatment 'cycle' is defined as a course of treatment of 14 days starting with the intravenous administration of nivolumab on Day 1 of each cycle along with once daily oral intake of ibrutinib on all days.

It is anticipated that approximately 158 subjects for both Parts A and B would be enrolled.

Part B (Dose Expansion Cohorts) will be open for enrollment after the RP2D is determined in Part A. In Part B, further assessment of the RP2D will be explored in 4 subject populations to further evaluate the safety and clinical activity of ibrutinib in combination with nivolumab. During the expansion period, subjects with CLL/SLL with del 17p or 11q (Cohort B1), FL (Cohort B2), DLBCL including FL transformed into DLBCL (transformed DLBCL) (Cohort B3), and Richter syndrome (Cohort B4) will be enrolled. Approximately 35 subjects will be

enrolled in each of the expansion cohorts. The subjects will be treated at the RP2D level selected to further assess the safety, pharmacokinetics, pharmacodynamics, pharmacogenomics, and activity of the combination.

The median duration of study therapy is expected to be approximately from 2 (DLBCL) to 15 (CLL) months.

The End-of-Treatment Visit will occur within 30 days after the last dose of ibrutinib or nivolumab, whichever treatment occurred last.

During the Follow-up Period, long-term safety, survival status, disease progression, subsequent anticancer therapy, and occurrence of other primary malignancy data will be collected. During the Follow-up Period, subjects should be followed for safety up to 30 days after the last dose of ibrutinib or 100 days after the last nivolumab infusion, whichever is later. The safety includes adverse event reporting and laboratory assessments (at the first follow up). Thereafter Follow-up visits will be completed approximately every 3 months until death or the end of study. Subjects who have developed treatment-related Grade 3 or higher toxicity at the end of treatment will be assessed until recovery to Grade ≤ 1 or baseline, deemed irreversible, or until end of study. Adverse events leading to discontinuation will be followed up until resolution or return to baseline, or end of study, whichever occur first.

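### Off-treatment scan schedule before progression is contradictory: every 10 weeks to month 15 in Attachment 5, but only 6-monthly in Table 1 and Sections 3.1 and 10.1, so PFS, DOR and response in early stoppers may be measured on either

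*Protocol*

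**What the plan says.** Four places in the current protocol set the imaging schedule for a subject who stops study treatment before progression.

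- **Attachment 5, Radiographic Image Assessments:** such subjects "must continue to have regularly scheduled CT scans/efficacy assessments every 10 weeks up to 15 months after the start of study drug". After that, "scan will be performed every 24 weeks until disease progression, or death, or the end of the study, whichever occurs first". Starting a new therapy is not a stopping point here.
- **Table 1, CT imaging row:** "During Follow-up, to be performed at PD and at least Q6 months up to PD or start of subsequent therapy".
- **Section 10.1:** "disease assessments will continue in the Follow-up Period at least every 6 months until disease progression is documented or the start of subsequent therapy". Earlier in the same paragraph, assessments are to run until progression "even if subsequent therapy is started prior to objective disease progression".
- **Section 3.1:** response is evaluated "at the end of treatment, and every 6 months in follow-up, in the event the subject has not progressed while on therapy" and has not started another therapy. This gives a flat 6 months, plus an end-of-treatment evaluation that the CT row of Table 1, as extracted, does not name.

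Section 11.2 says that scheduled assessments continue after such a stop but gives no interval. No passage states which text prevails.

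The SAP uses these assessments directly. PFS and DOR are censored at the last adequate disease assessment (4.3.1, 4.3.3). ORR counts any response up to the start of subsequent anti-cancer therapy (4.2.1), which includes one first seen after study treatment has stopped.

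**The concern.** Two sites can treat the same early stopper differently and both point to protocol text. A site working from Attachment 5 keeps the on-treatment rhythm. A site working from Table 1 may move the subject from 10-weekly to 6-monthly imaging, and the trigger is that treatment stopped. Progression is then looked for less often in subjects who came off drug early, and recorded PFS and DOR lengthen for a reason unrelated to the disease. The 1-year PFS rate is a stated secondary objective.

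The wording that 6 months is a minimum does not remove the conflict. A site scanning every 10 weeks satisfies Table 1 and Section 10.1, but a site scanning every 6 months breaches the mandatory wording of Attachment 5.

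The stopping points also disagree. Attachment 5 continues through a new therapy, Table 1 stops at it, and Section 10.1 says both.

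**Working it through.** **Inputs.** Cycle length is 14 days (Section 6.1). On-treatment scans are every 5 cycles from Cycle 5 to month 15, then every 12 cycles (Table 1, Attachment 5). One month is 30.4375 days and one year 365.25 days (SAP 2.7). The documents give no PFS assumption, so exponential progression with a median of 3 to 6 months is my assumption.

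**The plan's own intervals reproduce.** 5 x 14 = 70 days = 10 weeks. 12 x 14 = 168 days = 24 weeks. The first scan is at Cycle 5 Day 1 = 1 + 4 x 14 = Day 57, that is, 8 weeks after first dose.

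**Size of the gap.** 6 months = 6 x 30.4375 / 7 = 26.1 weeks, and 15 months = 65.2 weeks. To month 15 the intervals are 10 against 26.1 weeks, a ratio of 2.6. After month 15 they are 24 against 26.1 weeks, which hardly differs. The conflict therefore matters only in the first 15 months.

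**Scan dates for a subject who stops at week 8 without progression:**

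| Schedule | Later scans to month 15 (weeks) | Last scan before 1 year (52.2 weeks) |
|---|---|---|
| Attachment 5 | 18, 28, 38, 48, 58 | 48 |
| 6 months from the stop | 34.1, 60.2 | 34.1 |
| 6-month rule plus end-of-treatment scan at week 12 | 12, 38.1, 64.2 | 38.1 |

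**Recorded 1-year PFS.** Assume that progression is found only at scheduled scans, with no deaths, new therapy or clinically prompted scans. A subject is then recorded as progression-free at 1 year if progression comes after the last scan before week 52.2. With median M weeks, given no progression by week 8, the share is 2^(-(t - 8)/M), where t is that last scan. For the true rate, t = 52.2. A median of 3 months is M = 13.04, and 6 months is M = 26.09.

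| | Median 3 months | Median 6 months |
|---|---|---|
| True, t = 52.2 | 9.6% | 30.9% |
| Attachment 5, t = 48 | 11.9% | 34.6% |
| 6-month rule, t = 34.1 | 25.0% | 50.0% |
| 6-month rule plus end-of-treatment scan, t = 38.1 | 20.2% | 45.0% |

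Simulation under the same assumptions gives a mean delay from progression to detection of 5.8-6.9 weeks under Attachment 5 and 14.5-16.0 weeks under the 6-month rule.

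**The case against.** **Six months may be what the sponsor intended.** The Amendment 5 summary describes setting follow-up assessments at a minimum of every 6 months. It lists Table 1 and Sections 3.1 and 10.1 among the places changed, but not Attachment 5. Attachment 5 may simply have been left unrevised. This stands as a caution about the remedy. The current texts still conflict.

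**The numbers are close to a worst case.** Table 1 also calls for a scan at progression, and 3-monthly follow-up visits include a physical examination for disease assessment. Deaths and prompted scans would shorten the lag. The Section 3.1 end-of-treatment evaluation alone lowers 25-50% to about 20-45%. All of this stands, and the figures should be read as upper-end.

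**The trial is late.** The Amendment 7 summary says that the primary and secondary objectives have been analyzed and published. Table 1 has its own post-cutoff imaging rule. Any correction has little prospective effect. This also stands, and moves the emphasis to how the collected data are reported.

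**Stronger readings that a reader might infer, but that the documents do not support:**

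- *Many DLBCL subjects go 6 months with no post-baseline scan.* The SAP says "The median duration of study therapy is expected to be approximately from 2 (DLBCL) to 15 (CLL) months". That median covers every reason for stopping, and no share without progression is given. Two months is 60.9 days, after the Day 57 scan, and Section 3.1 adds an evaluation at end of treatment.
- *Early stoppers fall out of the response-evaluable set.* SAP 2.4.1 keeps subjects with no scan because of a possibly related adverse event, clinical progression or death, which covers most of this. In the all-treated analysis a missed response counts as non-response, which is conservative.
- *All early stoppers count as progression-free at 6 months.* Those without a later scan at cutoff are censored at their last adequate assessment, and the PFS objective is at 1 year.

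**Conclusion.** The contradiction is real and sits in operative text. PFS, DOR and response in subjects who stop without progression may be measured on either of two schedules. It would go too far to say that they are in fact measured on both, because the documents do not show which passage sites followed.

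For an early stopper at week 8, the choice of schedule moves recorded 1-year PFS by roughly 13 to 15 percentage points (11.9% to 25.0%, 34.6% to 50.0%). With an end-of-treatment scan the shift is about 8 to 10 points (11.9% to 20.2%, 34.6% to 45.0%). This rests on the assumed exponential progression, the assumed medians and detection at scheduled scans only.

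The effect on a whole cohort is smaller and cannot be computed, because the documents give no proportion of subjects stopping early without progression. The sample size is unaffected. The point should be corrected, but it does not make ORR or PFS unusable.

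**What to change.** 1. State one post-treatment assessment schedule and one stopping point (progression only, or progression or subsequent therapy) in Attachment 5, Table 1 and Sections 3.1 and 10.1. Resolve the internal conflict in Section 10.1 at the same time. Keep the post-cutoff rule in Table 1 (every 12 cycles or local standards, at least every 26 weeks).
2. For measurement, the Attachment 5 interval is preferable: it is the same on and off treatment, and those scans are already mandated. If the sponsor keeps 6 months, Attachment 5 must be changed, and the less frequent off-treatment assessment stated wherever PFS and DOR are reported.
3. Add the Section 3.1 end-of-treatment response evaluation to the CT row of Table 1.
4. For data already collected, report PFS and DOR together with the actual off-treatment scan intervals.

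The cost is protocol wording, one descriptive summary of scan intervals, and a few extra scans where sites had followed Table 1. Little changes prospectively after the clinical cutoff.

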18. Histologically confirmed initial diagnosis of FL of Grade 1, 2, or 3a according to World Health Organization (WHO) criteria without pathological evidence of transformation.
19. Relapsed or refractory disease defined as:
 - Previously treated with at least 2 prior lines of therapy using different treatment regimens and separated by disease progression or relapse
 - Received or not eligible for prior treatment with a CD20 antibody combination chemotherapy regimen
20. At least 1 measurable site of disease according to the Lugano Classification ([Attachment 6.2](#)).

Cohort B3: Diffuse Large B-cell Lymphoma

21. Histologically-confirmed DLBCL.
22. Previously treated with a standard, rituximab and anthracycline-containing systemic chemotherapy regimen (such as R-CHOP), or
Received or not eligible for high-dose chemotherapy and autologous stem cell transplantation (HD-ASCT)
Of Note: Additional, prior salvage chemotherapy regimens are allowed
23. At least 1 measurable site of disease based on the Revised Response Criteria for Malignant Lymphoma ([Attachment 6.2](#)).

Cohort B4: Richter Syndrome

24. Histologically-confirmed Richter syndrome defined as transformation of CLL or SLL into an aggressive lymphoma
25. Previously treated with at least one line of standard, systemic chemotherapy or not eligible for standard therapy
26. At least 1 measurable site of disease based on the Revised Response Criteria for Malignant Lymphoma ([Attachment 6.2](#)).

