PET using [18F]-fluorodeoxyglucose (FDG) is important for the complete assessment of response and progression in subjects with DLBCL. Whole body FDG-PET scan (skull base to the proximal femur) is recommended at Screening, at the time of maximal tumor reduction (eg, CR or 2 consecutive CT scans showing no further tumor reduction), and relapse from CR. For subjects with PET-negative tumors at baseline, the response evaluation will be based on the CT scan.

Assessment of PET results is based on published criteria.

Visual assessment is considered adequate for determining whether a PET scan is positive, and use of the standardized uptake value is not necessary. A positive scan is defined as focal or diffuse FDG uptake above background in a location incompatible with normal anatomy or physiology, without a specific standardized uptake value cutoff. Other causes of false-positive scans should be ruled out. Exceptions include mild and diffusely increased FDG uptake at the site of moderate- or large-sized masses with an intensity that is lower than or equal to the mediastinal blood pool, hepatic or splenic nodules 1.5 cm with FDG uptake lower than the surrounding liver/spleen uptake, and diffusely increased bone marrow uptake within weeks after treatment.

Bone Marrow Assessment

Bone marrow aspirate is mandatory and biopsy is optional at Screening (see [Table 1](#)). Subjects with bone marrow involvement must have a repeat bone marrow evaluation at the time of CR (preferably within 30 days of the initial documentation of CR). If bone marrow involvement can be confirmed with morphology, IHC or flow cytometry need not be done; 1 bone marrow examination is necessary for complete documentation of the CR.

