NOTE. Extent of disease is determined by positron emission tomography–computed tomography for avid lymphomas and computed tomography for nonavid histologies. Tonsils, Waldeyer's ring, and spleen are considered nodal tissue.

a: Whether stage II bulky disease is treated as limited or advanced disease may be determined by histology and a number of prognostic factors.

Criteria for Response Assessment of Non-Hodgkin's Lymphoma

| Response | Site | PET-CT-Based Response | CT-Based Response |
|-----------------|--------------------------------------|--|---|
| Complete | Lymph nodes and extralymphatic sites | Complete metabolic response | Complete radiologic response (all of the following) |
| | | Score 1, 2, or 3 ^a with or without a residual mass on 5PS ² It is recognized that in Waldeyer's ring or extranodal sites with high physiologic uptake or with activation within spleen or marrow (eg, with chemotherapy or myeloid colony-stimulating factors), uptake may be greater than normal mediastinum and/or liver. In this circumstance, complete metabolic response may be inferred if uptake at sites of initial involvement is no greater than surrounding normal tissue even if the tissue has high physiologic uptake | Target nodes/nodal masses must regress to ≤ 1.5 cm in LDi No extralymphatic sites of disease |
| | Non measured lesion | Not applicable | Absent |
| | Organ enlargement | Not applicable | Regress to normal |
| | Bone marrow | No evidence of FDG-avid disease in marrow | Normal by morphology; if determinate, IHC negative |
| Partial | Lymph nodes and extralymphatic sites | Partial metabolic response | Partial remission (all of the following) |
| | | Score 4 or 5 ^b with reduced uptake compared with baseline and residual mass(es) of any size At interim, these findings suggest responding disease At end of treatment, these findings indicate residual disease | $\geq 50\%$ decrease in SPD of up to 6 target measurable nodes and extranodal sites When a lesion is too small to measure on CT, assign 5 mm \times 5 mm as the default value When no longer visible, 0 \times 0 mm For a node > 5 mm \times 5 mm, but smaller than normal, use actual measurement for calculation |
| | Nonmeasured lesion | Not applicable | Absent/normal, regressed, but no increase |
| | Organ enlargement | Not applicable | Spleen must have regressed by $> 50\%$ in length beyond normal |

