- ^a: A score of 3 in many patients indicates a good prognosis with standard treatment, especially if at the time of an interim scan. However, in trials involving PET where de-escalation is investigated, it may be preferable to consider a score of 3 as inadequate response (to avoid undertreatment). Measured dominant lesions: Up to six of the largest dominant nodes, nodal masses, and extranodal lesions selected to be clearly measurable in two diameters. Nodes should preferably be from disparate regions of the body and should include, where applicable, mediastinal and retroperitoneal areas. Non-nodal lesions include those in solid organs (eg, liver, spleen, kidneys, lungs), GI involvement, cutaneous lesions, or those noted on palpation. Nonmeasured lesions: Any disease not selected as measured, dominant disease and truly assessable disease should be considered not measured. These sites include any nodes, nodal masses, and extranodal sites not selected as dominant or measurable or that do not meet the requirements for measurability but are still considered abnormal, as well as truly assessable disease, which is any site of suspected disease that would be difficult to follow quantitatively with measurement, including pleural effusions, ascites, bone lesions, leptomeningeal disease, abdominal masses, and other lesions that cannot be confirmed and followed by imaging. In Waldeyer's ring or in extranodal sites (eg, GI tract, liver, bone marrow), FDG uptake may be greater than in the mediastinum with complete metabolic response, but should be no higher than surrounding normal physiologic uptake (eg, with marrow activation as a result of chemotherapy or myeloid growth factors).
- ^b: PET 5PS: 1, no uptake above background; 2, uptake \leq mediastinum; 3, uptake $>$ mediastinum but \leq liver; 4, uptake moderately $>$ liver; 5, uptake markedly higher than liver and/or new lesions; X, new areas of uptake unlikely to be related to lymphoma.

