7.5.6. Biomarker Data Analysis Methods for Flow Cytometry T-cell Type Panel Data

- Data arising from T-cell type panel collected over time will be descriptively summarized for each biomarker stratification cohorts. The corresponding mean (\pm se) over time line plot for each biomarker stratification cohorts will be generated. In Addition, mean change and percent change from baseline will also be descriptively summarized. The corresponding mean change and percent change from baseline values will be plotted.

- Mean values for each T- cell type over times by response group (i.e., non-responder and responder) will be reported for the biomarker stratification groups – CLL, FL, DLBCL, ABC-DLBCL, GCB-DLBCL and Richter's. For each cell type, the corresponding mean (\pm se) line and box plots over time by response group for each selected biomarker stratification group will be generated. Similarly, the mean (\pm se) line plot over time by progression group (i.e., progressor and non-progressor) for each cell type for selected biomarker stratification group will also be generated.
- Paired t-test will be performed to compare the mean at baseline vs the mean at each post baseline time point for each cell type and for each selected biomarker stratification group by respond group and progression group, respectively.

REFERENCES

APPENDICES

1. Appendix A

Preferred terms for CNS hemorrhage are as follows:

- Acute haemorrhagic leukoencephalitis
- Basal ganglia haemorrhage
- Brain stem haemorrhage
- Brain stem haematoma
- Central nervous system haemorrhage
- Cerebellar haematoma
- Cerebellar haemorrhage
- Cerebral arteriovenous malformation haemorrhagic
- Cerebral haematoma
- Cerebral haemorrhage
- Cerebral microhaemorrhage
- Encephalitis haemorrhagic
- Epidural haemorrhage
- Extradural haematoma
- Haemorrhage intracranial
- Haemorrhagic cerebral infarction
- Haemorrhagic stroke
- Haemorrhagic transformation stroke

- Intracerebral haematoma evacuation
- Intracranial haematoma
- Intracranial tumour haemorrhage
- Intraventricular haemorrhage

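### Attachments 5 and 6.2 of the protocol set different PET thresholds, so CR status and best response can depend on which one the investigator follows

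*Protocol*

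**What the plan says.** **Governing criteria.** Protocol Section 10.1 (Table 21) assigns Lugano, Attachment 6.2, to Part A B-cell NHL including SLL, to the SLL subjects of B1, and to B2, B3 and B4. SAP Section 4.1.3 does the same by disease. CLL is assessed by IWCLL and is outside this point.

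**Attachment 6.2.** Scores 1, 2 or 3 are a complete metabolic response "with or without a residual mass on 5PS". Footnote b defines the scale: 1 is no uptake above background, 2 is up to mediastinum, 3 is above mediastinum and up to liver, 4 is moderately above liver, and 5 is "uptake markedly higher than liver and/or new lesions".

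**Attachment 5.** Section 10.1 refers sites here for the detail of the efficacy measurements. PET is read visually: "A positive scan is defined as focal or diffuse FDG uptake above background in a location incompatible with normal anatomy or physiology". One exception covers mild, diffuse uptake in moderate or large masses "with an intensity that is lower than or equal to the mediastinal blood pool". Two others cover certain liver or spleen nodules and diffuse marrow uptake soon after treatment. The stated source is only this: "Assessment of PET results is based on published criteria". The 5-point scale is not mentioned. Attachment 5 also gives baseline PET status a role: "For subjects with PET-negative tumors at baseline, the response evaluation will be based on the CT scan".

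**The concern.** The response criteria place the line between complete and incomplete metabolic response at liver uptake. The procedures attachment places the line for a positive scan at background, or at mediastinal blood pool for larger masses. Both are written as operative rules and neither yields to the other.

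PET is scheduled at maximal tumor reduction and at relapse from CR, which is when CR is assigned or lost. Reads are by investigators in an open-label study. Section 10.1 allows independent review of the scans only if thought necessary, so no routine central read would bring sites onto one rule. At stake are the CR rate, best response (SAP Section 2.7 ranks CR first and PR third) and its date, and clarity about when a CR has ended.

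**Working it through.** **Step 1. The two rules side by side, for a post-baseline residual lesion outside the liver/spleen-nodule and marrow exceptions.**

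| Uptake | 5-point score | Attachment 5 | Attachment 6.2 | Agree? |
|---|---|---|---|---|
| Not above background | 1 | not positive | complete metabolic response | yes |
| Above background, up to mediastinum; mild and diffuse in a moderate or large mass | 2 | not positive (exception) | complete metabolic response | yes |
| Above background, up to mediastinum; small lesion | 2 | positive | complete metabolic response | **no** |
| Above mediastinum, up to liver | 3 | positive | complete metabolic response | **no** |
| Above liver | 4 or 5 | positive | not complete | yes |

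The conflict is confined to score 3 and to score 2 in small lesions.

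**Step 2. What follows for ORR.** ORR is CR plus PR. Take a score-3 lesion, CR under Attachment 6.2, that a site reads as positive:

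- Sum of products (SPD) down by 50% or more, with the other CT conditions met: PR by CT. Responder either way; ORR change 0.
- SPD down by less than 50%, scan treated as residual disease with reduced uptake: PR. ORR change 0.
- SPD down by less than 50%, site classifies by CT instead: stable disease. One responder lost.

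Only the third branch changes ORR. Attachment 5 assigns no response category to a positive scan, and its switch to CT is for tumors that were PET-negative at baseline, so the documents do not direct that branch.

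**Step 3. Size of the sub-case.** First, the plan's own sample size. Inputs from protocol Section 12.3: ORR 20% versus 38%, one-sided alpha 0.1, power at least 0.8, 32 evaluable subjects. Exact binomial, success if X ≥ 10 of 32:

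- P(X ≥ 10 | 0.20) = 0.0898
- P(X ≥ 10 | 0.38) = 0.833
- n = 31 gives power 0.799, so 32 reproduces.

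One lost responder moves a cohort's ORR by 1/32 = 3.1 percentage points, or 1/35 = 2.9 points on all enrolled. The documents give no share of score-3 scans, so the shares below are assumptions for illustration only:

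| Assumed share of cohort losing responder status | Rate used | P(X ≥ 10 of 32) |
|---|---|---|
| 0 | 0.38 | 0.833 |
| 3% | 0.35 | 0.732 |
| 5% | 0.33 | 0.648 |
| 10% | 0.28 | 0.405 |

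**The case against.** The strongest reply is that the governing criteria are not in doubt. The synopsis, protocol Sections 3.1 and 10.1 and SAP Section 4.1.3 all name Lugano. Attachment 5 is titled as procedures and Attachment 6 as response criteria. Attachment 6.2 never defines a positive PET; its liver threshold is implied by its response categories, and its table on site involvement speaks only of increased uptake, which is compatible with Attachment 5. The protocol's explicit uses of PET-positive and PET-negative are at baseline. This largely stands, and it limits the point to a rule that competes with clearly named criteria. It does not remove the conflict: Attachment 5 applies its definition to scans generally, includes a post-treatment marrow exception, and never points to the 5-point scale.

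Three stronger readings are tempting, and the documents do not support them.

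- A reader might infer that responder status in general turns on the attachment used. CR to PR leaves ORR unchanged, and the route to non-response needs a fallback to CT that no section directs.
- A reader might infer that a rise from score 2 to 3 is a relapse, and so a PFS or DOR event, under Attachment 5. That attachment gives no relapse rule, and PET progression in Attachment 6.2 needs score 4 or 5 with increased uptake, or new avid foci.
- A reader might infer that all subjects of B2, B3 and B4 (3 × 35 = 105 planned) are affected. Table 1 makes baseline PET recommended rather than mandatory, Attachment 5 ties follow-up PET to baseline positivity, and only some of those scans fall in the discordant band.

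Criteria 23 and 26 ("At least 1 measurable site of disease based on the Revised Response Criteria for Malignant Lymphoma") and the SAP reference list ("Revised response criteria for malignant lymphoma") show mixed versions of the criteria, but they are weak evidence here. The two criteria concern measurability and point to Attachment 6.2, and a reference entry does not override SAP Section 4.1.3.

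**Conclusion.** The conflict is in the text and is not reconciled. For Lugano-assessed subjects who have PET, a score-3 residual lesion, or a small lesion at score 2, can be recorded as CR or not according to the attachment followed. CR rate and best response are directly exposed, and the date at which CR is lost may be blurred. Departures run one way: Attachment 5 is the stricter rule, so following it lowers the CR count relative to Lugano.

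The effect on ORR is conditional and cannot be sized from the documents. The power figures above assume both the share of subjects and the CT fallback; they show sensitivity and are not an estimate. The point merits correction because the remedy is specific and cheap, not because the primary result is shown to be at risk.

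**What to change.** 1. In Attachment 5, state that post-baseline PET response is read on the 5-point scale and assigned to the categories of Attachment 6.2. Delete the positive-scan paragraph, or limit it so that it does not govern response.
2. State separately which rule sets baseline PET-positive or PET-negative status, since that status selects who has follow-up PET and whose response is CT-based. Do not carry the 1–3 versus 4–5 split over to baseline by default: it would send a tumor at score 3 at baseline to the CT route. At the same time, align Table 1 and the two parts of Attachment 5 on whether screening PET is required or recommended.
3. As tidy-up, name Lugano in criteria 23 and 26, and put the Lugano paper in the SAP reference list.
4. Amendment 7 says the primary and secondary objectives have been analyzed and published, so new wording cannot change those reads. Where a 5-point score or source PET report is available, check the CR labels and report any reclassification of CR or best response, and of ORR if any occurs.

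Items 1 to 3 cost protocol and SAP wording and a letter to sites, with no new scans. The cost of item 4 depends on what was recorded: no section shows that the eCRF holds a 5-point score.
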